13.0 Statistical Considerations

13.1Study Design

Our target sample size for this study will be 200 caregiver-patient dyads (after 20% attrition). The planned sample size is 100 caregiver-patient dyads per treatment group. The power of statistical tests (two-sided 0.05 level of significance) is shown below for the primary outcomes of each specific aim. The effect sizes are shown as pairs of numbers representing the expected control group mean, based on published data, and the hypothetical population mean for the intervention care group. The SD column is based on published data, and power is conservatively estimated for a simple t-test on a single post-intervention measurement. The planned analysis, described in section E.5, will adjust for baseline values, and will combine longitudinal assessments, both of which will improve power.

A total of 80 new cases of stage I-III surgically treated NSCLC were available at City of Hope in fiscal year 2015. Our institutional race distribution is 56.2% Caucasian, 20.5% Hispanic, 4.7% Black, 13.5% Asian, and 5.1% other (38.7% ethnic minorities overall). These statistics should reflect the anticipated race distribution for participants. All efforts will be made to accrue minorities. Our pilot study demonstrates that we are able to accrue minorities (38%) to match the population at City of Hope.

A sample size of 100 per arm was calculated, based primarily on outcome means and variation observed in our previous studies (see Section E.1 for sample size calculations and power analysis). We have projected attrition based on previous studies. We will enroll 100 participants per arm to allow for 20% drop-out/attrition during the course of the study. We will enroll a total of 200 dyads in order to retain 160 dyads at 3-months. With a 52 month accrual plan, we estimate that 4 caregiver-patient dyads will need to be accrued per month. With a total pool of 80 potential dyads per year, this yields approximately 7 dyads per month that are eligible for the study. Hence, we will have a sufficient pool of eligible participants for study accrual. In our lung cancer Program Project (N=366), we were able to enroll 4 FCGs and patients per month. ^{59, 114}

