We will study FCGs and patients age 21 and over to obtain participants across a spectrum of chronological ages. A range of ages is expected although we anticipate at least 68% of NSCLC patients will be \geq 65 years. We anticipate that the majority of FCGs will be spouses and \geq 60 years old given the patient age distribution. Based on our experiences, 90% of patients have an identified FCG. We acknowledge that the aging spectrum is heterogeneous and that older patients have a higher risk of surgical morbidity. We anticipate that the majority of FCGs will be female (75%), but expect an equal representation by sex for patients. We recognize that age and sex are important influencing factors. We will examine the moderating effect of these biological variables on outcomes in Exploratory Aim 1.

IRB 17238 02/02/2023

Specific Aim 1 addresses the effects of the MSM Intervention on FCG outcomes, and **Table 3** provides FCG outcome effect size and power based on 80 participants per group. **Hypothesis 1.1** will address FCGs' psychological distress and burden. The study by Zwahlen et

Table 3. FCG Outcomes Effect Size and Power

Outcome	Measure	Effect	SD	Power
H1.1 Psychological distress	Distress thermometer	3.7 v 2.5	2.6	83%
H1.1 Caregiver burden	Objective burden score	22.0 v 20.2	4.0	81%
H1.2 Caregiver preparedness	Preparedness score	3.7 v 4.1	0.72	93%
H1.2 Caregiver QOL	Total QOL score	5.9 v 6.6	1.42	87%
H1.3 Social work referrals	FCG healthcare use	20% v 40%	NA	80%
H1.3 FCG center resource use	FCG healthcare use	30% v 60%	NA	97%

al⁷¹ provides distress thermometer (DT) scores for 306 family members, including 32 relatives of lung cancer patients. The mean score was 3.7, and the standard deviation was 2.6. With this SD, a reduction of the mean by 1.2 points could be detected

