Data management is of key importance in this study. Our institutional research informatics core will develop an electronic data entry, capture, and storage system that will perform tracking functions (accrual, enrollment, consenting, data collection, and intervention delivery). We will develop a query system to address data validity and integrity by making early identification of cases of recruitment irregularity, data collection inconsistency, data inaccuracy or incompleteness. Data will be audited for accuracy prior to scoring and analysis.

Our primary data analysis will be according to intention-to-treat, i.e. all participants will be included in the analysis whether or not they received all prescribed intervention components. Participants who are lost to follow-up due to mortality will not be included. Reasons for study dropout will be recorded. Participants with missing items will be compared with those having non-missing items to determine whether missing data are random or can be accounted for by other variables. Broadly, our data may be missing at random (MAR) or missing not at random (MNAR). Generalized linear model with robust (sandwich) variance estimator model will be fitted to the data, with time, baseline, treatment arms, and interaction of time and treatment as explanatory variables. This approach provides valid standard errors with repeated measurement of individuals. It also accommodates missing time points by using the model of time effects to reduce bias. For MNAR, a pattern mixture model⁵⁵ will be fitted to the data to correct for informative drop-out. In particular, three patterns will be defined: a pattern consisting of participants who died during the study period, a pattern of participants with relapse, and a pattern of participants who remained disease free. Within each pattern, data will be modeled by the random effects model. To compare treatment arms, the effects of both arms will be respectively estimated using a weighted average across all patterns weighted by their sample proportions.

IRB 17238 02/02/2023

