These two hypotheses will be tested in the same way. We will address the effect of the intervention on FCG psychological distress, burden, preparedness for caregiving, and QOL at months 1 and 3, adjusted for baseline response. Scores for all outcome measures will initially be summarized graphically and numerically at baseline, month 1, and month 3, for each stratum, along with simple diagnostic plots. The need for transformation will be accessed. A generalized linear mixed model will be fit to estimate the distribution of 1 month and 3 month score as a function of treatment, stratum, occasion (month 1 or 3) and baseline value. The robust (sandwich) variance estimator will be used to accommodate the correlation of the two occasions, and the estimated treatment effect for the adjusted average of the 1 and 3 month outcomes will be estimated and tested, in order to limit multiplicity with respect to occasions, and to improve upon the designed power by combining information, effectively reducing standard deviations relative to those used for planning. This is similar to the analysis of average outcome for the two post-treatment occasions, except that it accommodates missing outcome evaluations by attributing observations to the appropriate occasion (comparing like with like), and avoids overstating information. Analysis of average outcome does provide a convenient robustness check. Each analysis will be a repeated measures ANCOVA statistical design, removing variances prior to examining mean squares for the group by occasion interactions, and covarying the baseline scores. The independent variable will be group (intervention vs. attention control). Hypothesis 1.3: The intervention group will have higher social work referrals and family resource center use.

FCG cancer support services will be evaluated by recording social work referrals and family resource center use. Each subject will be classified as having an event or not. There is no baseline value, but the data will be tabulated by surgery stratum, and tested for homogeneity (interaction) before estimating and testing the overall treatment effect.

IRB 17238 02/02/2023

Specific Aim 2: Test the effects of the MSM Intervention on patient outcomes and healthcare resource use at discharge and 3-months post-discharge, comparing intervention and attention control groups.

Hypothesis 2.1: The intervention group will experience lower psychological distress and higher OOL.

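### E.5 gives two different tests for the same score hypotheses, the adjusted average effect and the group-by-occasion interaction, and does not say which one decides

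*Combined protocol and SAP*

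**What the plan says.** All of this is in section 13.0 of the combined protocol and SAP.

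- **General rule (opening of E.5).** Each outcome gets a confidence interval and a test for the effect of treatment, with the randomisation stratum and the baseline value as covariables.
- **Aim 1, Hypotheses 1.1 and 1.2.** The month 1 and month 3 scores are modelled "as a function of treatment, stratum, occasion (month 1 or 3) and baseline value". The treatment effect on the adjusted average of the two months is to be estimated and tested. The reasons given are to limit multiplicity over occasions and to gain power. A simple analysis of each person's average serves as a robustness check. The same paragraph then states that each analysis will be a repeated measures ANCOVA, "removing variances prior to examining mean squares for the group by occasion interactions, and covarying the baseline scores".
- **Aim 2, Hypothesis 2.1, and Aim 3, Hypothesis 3.1.** Both adopt the Aim 1 plan by reference and repeat the interaction sentence in full. The average effect is not written out again.
- **Missing-data paragraph, before E.4.** A generalized linear model is listed "with time, baseline, treatment arms, and interaction of time and treatment as explanatory variables". Stratum is not in that list, and no test term is named.

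No sentence ranks the average effect against the interaction.

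**The concern.** A group-by-occasion interaction carries the treatment effect when baseline is one of the occasions, because the groups start level and then diverge. Here baseline has moved to the covariate side and the occasions are months 1 and 3. The interaction therefore compares the effect at month 3 with the effect at month 1. A benefit of equal size at both months cancels out of it, and adding another post-baseline occasion such as discharge would not change that.

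The protocol overview (section 2.2) names a sustained effect at 3 months as a target, and the interaction does not test for one. An analyst who took the repeated ANCOVA sentence as the decision rule would test something other than the hypotheses as written. The choice between the two terms is also unprotected, since E.5 applies 0.05 to each outcome without adjustment. The ambiguity covers every score outcome in Aims 1 to 3.

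**Working it through.** **Inputs from the documents**
- Two-sided 0.05: "The power of statistical tests (two-sided 0.05 level of significance) is shown below for the primary outcomes of each specific aim".
- Basis of the stated power: "power is conservatively estimated for a simple t-test on a single post-intervention measurement".
- Table 3 "provides FCG outcome effect size and power based on 80 participants per group"; 100 per arm are enrolled to allow for 20% attrition.
- Caregiver distress: difference 1.2, SD 2.6, stated power 83%.

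**Assumed, because the documents give neither**
- ρ, the correlation between the month 1 and month 3 scores.
- r, the correlation of baseline with each follow-up score.

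The SD is taken as equal at both months. The main range is r = ρ = 0.3 to 0.7.

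**Step 1: reproduce the plan's figure.** SE = 2.6 × √(2/80) = 0.411. Then 1.2/0.411 = 2.92, and Φ(2.92 − 1.96) = 83.1%, against 83% stated (82.7% with the noncentral t). The plan's figure is therefore power for a difference in means, not for an interaction.

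**Step 2: variance per person of each contrast, given baseline**
- Average of the two months: SD² × [(1 + ρ)/2 − r²].
- Month 3 minus month 1: 2 × SD² × (1 − ρ). Baseline drops out because it correlates equally with both months.

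In each case SE = √(2 × variance/80) and power ≈ Φ(|effect|/SE − 1.96), plus the opposite tail.

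**Step 3: numbers at r = ρ = 0.5**
- Average: variance 6.76 × (0.75 − 0.25) = 3.38, SE 0.291. A constant 1.2 gives 1.2/0.291 = 4.13 and power 98.5%.
- Interaction: variance 2 × 6.76 × 0.5 = 6.76, SE 0.411. A constant 1.2 makes the contrast 1.2 − 1.2 = 0, so it rejects at alpha, 5%.
- Benefit of 1.2 at month 1 and 0 at month 3: the interaction contrast is 1.2 (83.1%) and the average effect is 0.6 (54.1%).

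**Step 4: the assumed range**

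| r = ρ | Constant 1.2: interaction | Constant 1.2: average | 1.2 then 0: interaction | 1.2 then 0: average |
|---|---|---|---|---|
| 0.3 | 5% | 97.4% | 69.4% | 49.6% |
| 0.5 | 5% | 98.5% | 83.1% | 54.1% |
| 0.7 | 5% | 99.8% | 96.5% | 68.2% |

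Over a wider grid (r from 0 to 0.7, ρ from 0.3 to 0.9), the average test has 85% to over 99% power for the constant benefit, and the interaction stays at 5%.

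**Step 5: simulation check.** 10,000 ANCOVA runs at r = ρ = 0.5:
- Constant benefit: average 98.3%, interaction 5.15%.
- Fading benefit: average 53.5%, interaction 81.4%.

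**Step 6: cost of leaving the choice open.** With equal variances and equal baseline correlations at the two months, the average and the difference are uncorrelated. If significance on either counts, null error per outcome is about 1 − 0.95² = 9.75%.

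**The case against.** The strongest reply is that the plan already contains the right test. Aim 1 commits to testing the adjusted average effect and gives reasons and a robustness check. Aims 2 and 3 take that plan over, and the general rule of E.5 is a test of the treatment effect. The interaction is only to be examined, the next sentence names group as the independent variable, and the model listed under Aim 1 has no interaction term. On this view the disputed sentence is loose drafting.

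Much of that stands, and it rules out three stronger readings that a reader might infer:

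- *That the trial as planned detects a sustained benefit only at chance.* The 5% belongs to the interaction term. Under the average test in the same paragraph, power is about 97% or more over the main assumed range.
- *That the two tests behave in opposite ways, so that a lost effect is called positive and a sustained one negative.* For a benefit that fades to zero, the average test also rejects about half to two thirds of the time. The sharp divergence is confined to the constant effect.
- *That the missing-data model is a rival primary analysis, with a treatment coefficient that applies to one occasion only.* That paragraph names no test and no coding, and E.5 separately requires stratum. The missing stratum is a small point of alignment.

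The reply does not remove the ambiguity. The interaction sentence says what each analysis will be. It appears three times, and under Aims 2 and 3 it is the only term spelled out. Nothing marks it as secondary.

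**Conclusion.** The plan contradicts itself over which term tests Hypotheses 1.1, 1.2, 2.1 and 3.1. One of the two candidates, the interaction, does not address those hypotheses. That it rejects at 5% under a constant benefit follows from its definition and needs no assumption about correlations. The other rates rest on the planning values for caregiver distress, 80 analysed per group, equal variances at the two months, and assumed correlations of 0.3 to 0.7. The 9.75% also needs equal baseline correlations and applies only if either result would be accepted as a positive finding. The documents do not say that it would; they leave it open.

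This should be settled before the data are analysed, because it determines the deciding test for the main score outcomes. The point takes the occasions as E.5 gives them.

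**What to change.** 1. Under Aims 1, 2 and 3 in E.5, state that each score hypothesis is decided by the treatment effect on the adjusted average of months 1 and 3, as Aim 1 already specifies.
2. Delete the interaction sentence in all three places, or keep it as a labelled secondary check of whether the effect changes over time, with no bearing on whether a hypothesis is supported.
3. Add the randomisation stratum to the model listed in the missing-data paragraph so that it agrees with E.5.

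The cost is a wording amendment. Sample size and the stated power for a difference in means are unaffected, and no new data are needed.

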12.1.2 Subject Consent Form

Initial verbal consenting will only be used when potential participants are not in the clinic. In these situations, the Research Nurse and CRA will use the approved information sheet (available in both English and Chinese) for verbal consent process. An informed consent (available in both English and Chinese) will then be obtained either in writing in person, by mail, or electronic mail, or electronically via other electronic applications (i.e. DocuSignTM). Otherwise, all participants will complete either a written or electronic informed consent (i.e. DocuSignTM) prior to study participation. The study will use one written or electronic informed consent (with signature line) and one information sheet (without signature line) for FCGs, and one written or electronic informed consent (with signature line) and one information sheet (without signature line) for patients. Documentation of initial verbal consent for study participation will be charted through progress notes and maintained in the patients' electronic medical records as required by the Institutional Review Board.

12.1.3 Data Collection Forms and Submission Schedule

Table 2 provides outcome measures and the corresponding evaluation time points. All outcome measures completed by patients/FCGs are available and validated in both English and Chinese. We will collect sociodemographic and health status data (e.g. age, sex, race/ethnicity, education, employment, relationship to patient, religious preference, marital status, living

IRB 17238 02/02/2023

situation, income, co-morbidities, and tobacco history) for both FCGs and patients at baseline. Outcomes are assessed at baseline (before surgery), discharge, 1 month, and 3-months post-discharge. They will take about 30 to 45 minutes to complete. Outcomes were selected based on our conceptual model, previous research in lung cancer, and recommendations on common data elements for self-management research.⁹⁷

Table 2. Outcome Measures by Aims and Assessment Time Points								
	Measures	Baseline	Discharge	1 month	3 months			
	Distress Thermometer	X	X	x	х			
Family	Montgomery Borgatta Caregiver Burden Scale	х	Х	х	х			
Caregivers	Preparedness for Caregiving Scale	х	X	x	х			
Ü	COH-QOL-Family	х	X	х	х			
	Family Caregiver Healthcare Use Survey		X	х	х			
	Distress Thermometer	X	X	x	х			
Patients	FACT-L	X	Х	х	х			
	Patient Healthcare Use Survey (non-COH)			x	х			
	Medical Chart Audit Form				x			

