with 83% power. Caregiver burden is described by the research team's previous work¹¹⁴ with mean objective burden subscale scores of near 22.0, with a pooled standard deviation of 4.0. With 80 subjects per group, a reduction by 1.8 points could be detected with 81% power. **Hypotheses 1.2** address preparedness for caregiving and QOL. In our previous work, preparedness has been reported on a 1 to 5 scale with a mean of approximately 3.7 and SD of 0.72. An increase in mean score from 3.7 to 4.1 could be detected with 93% power. Total QOL scores for 157 FCGs are reported by our previous work¹¹⁴, with a mean total score of 5.93 and a standard deviation of 1.42. An increase in mean total QOL score of 0.7 could be detected with 87% power. **Hypothesis 1.3** address changes in FCG cancer support services use. Here, we will classify each FCG as to whether they had an encounter with social work services and family resource center. A difference of 20 percentage points for social work referrals and 30 percentage points for family resource center would be detectable with 80 subjects per group.

Specific Aim 2 addresses the effects of the MSM Intervention on patient outcomes, and **Table 4** provides patient outcome effect size and power. **Hypothesis 2.1** addresses patients' psychological distress and QOL, and **Hypothesis 2.2** addresses healthcare resource use. For each

Table 4. Patient Outcomes Effect Size and Power

Outcome	Measure	Detectable effect	SD	Power
H2.1 Psychological distress	Distress thermometer	3.5 v 2.4	2.4	82%
H2.1 QOL	FACT-L	93.7 v 101.3	17.0	80%
H2.2 Resource use	Any use (y/n)	53% v 31%	NA	80%

of these outcomes, the mean control group value, the root mean square (RMS) standard deviation, and the detectable improvements (Delta) in mean score was calculated

for a two-sided 0.05 significance level test using 80 subjects per group. For resource use, we will classify each patient as to whether they had in-home nursing care, urgent care/ER visits, or a readmission. In preliminary data, 20 of 38 subjects had such an event, indicating that a difference of 22 percentage point would be detectable with 80 subjects per group.

Specific Aim 3 addresses the effect of outcome mediators on FCG and patient outcomes

Table 5. Outcome Mediator Effect Size and Power

Outcome	Measure	Detectable effect	SD	Power
H3.1 Activation	PAM and FCAT	72.0 v 80.0	18.0	80%
H3.1 Self-Efficacy	Self-Efficacy Tool	20.0 v 22.0	22.0	80%
H3.1 Knowledge	Knowledge Tool	8.5 v 9.0	1.0	88%

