For this hypothesis, we will address patient psychological distress and QOL. Distress and QOL are each quantitative scales measured at both 1 month and 3 months. These will be analyzed by the same plan described for Specific Aim 1, hypothesis 1.1 and 1.2. Each analysis will be a repeated measures ANCOVA statistical design, removing variances prior to examining mean squares for the group by occasion interactions, and covarying the baseline scores. The independent variable will be group (intervention vs. attention control).

Hypothesis 2.2: The intervention group will have lower in-home nursing care, lower urgent care/ER visits, and lower hospital readmissions.

Similar to Specific Aim 1, hypothesis 1.3, patient healthcare resource use will be evaluated by recording in-home nursing care, urgent caregcp/ER visits, and readmissions (COH and non-COH encounters). Each subject will be classified as having an event or not. There is no baseline value, but the data will be tabulated by surgery stratum, and tested for homogeneity (interaction) before estimating and testing overall treatment effect.

Specific Aim 3: Test the effects of the MSM Intervention on outcome mediators at discharge and 3-months post-discharge, comparing intervention and attention control groups. **Hypothesis 3.1:** FCGs and patients in the intervention group will experience higher activation, self-efficacy, and knowledge.

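### H1.3 and H2.2 are analysed with the surgery stratum alone; pre-specifying a few baseline covariates already collected would gain some power at almost no cost

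*Combined protocol and SAP*

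**What the plan says.** Section E.5 (within 13.1) sets a general approach for each outcome: the treatment effect is estimated with the randomisation stratum and the outcome's own baseline value as covariables. The reasons given include a smaller residual variance and more power. For robustness it adds two secondary analyses: a comparison without covariables, and a three-covariable model with a propensity score for leftover imbalance in medical or socio-demographic variables.

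H1.3 and H2.2 depart from this. Under each the plan says "There is no baseline value, but the data will be tabulated by surgery stratum, and tested for homogeneity (interaction" and then proceeds to the overall treatment effect. No covariate other than stratum is named, and the test itself is not named.

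Section 12.1.3 states "We will collect sociodemographic and health status data", with age, co-morbidities and tobacco history among the examples. Table 2 there schedules the patient FACT-L and the caregiver distress and burden scales at baseline. Section 5.6 gives every participant a geriatric assessment, which section 10.0 schedules at baseline for both caregivers and patients.

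The power tables in 13.1 give 80% for social work referrals (20% v 40%), 97% for resource-center use (30% v 60%) and 80% for any patient resource use (53% v 31%). All are at 80 per group. The Synopsis lists support-service use and healthcare resource use among the primary endpoints.

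**The concern.** The plan gives up covariate adjustment for these endpoints because one particular covariate, the baseline value of the same outcome, does not exist. That does not follow. Any pre-randomisation variable that predicts the event can sharpen the comparison, and several plausible ones are already in the database. The plan itself links severe comorbidity to resource use after surgery (section 2.1) and older age to surgical morbidity (section 13.1).

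At stake is some power on two endpoints planned at about 80%. Validity is not at stake: a stratum-only comparison in a randomised trial is unbiased and controls type I error.

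**Working it through.** **Inputs.** Two-sided 0.05 ("The power of statistical tests (two-sided 0.05 level of significance) is shown below for the primary outcomes of each specific aim"). Enrolment: "The planned sample size is 100 caregiver-patient dyads per treatment group". Retention: "We will enroll a total of 200 dyads in order to retain 160 dyads at 3-months", that is 80 per arm, the figure behind the H1.3 statement ("would be detectable with 80 subjects per group") and the H2.2 table ("for a two-sided 0.05 significance level test using 80 subjects per group"). Event rates are from Tables 3 and 4.

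**Step 1: reproduce the stated power without covariates.** Pooled normal approximation, with d the difference and p̄ the mean of the two rates:

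power = Φ[(d − 1.96·se0)/se1], se0 = √(2p̄(1−p̄)/n), se1 = √((p1(1−p1)+p2(1−p2))/n), n = 80.

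- H2.2: d = 0.22, p̄ = 0.42, se0 = 0.0780, se1 = 0.0761. z = (0.22 − 0.1530)/0.0761 = 0.881, power 81.1% (stated 80%).
- Social work: d = 0.20, p̄ = 0.30, se0 = 0.0725, se1 = 0.0707. z = (0.20 − 0.1420)/0.0707 = 0.820, power 79.4% (stated 80%).
- Resource center: d = 0.30, p̄ = 0.45, se0 = 0.0787, se1 = 0.0750. z = (0.30 − 0.1542)/0.0750 = 1.944, power 97.4% (stated 97%).

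All three reproduce. Because the test is unnamed, the alternatives matter: a continuity correction gives 76.3%, 74.0% and 96.2%, and Fisher's exact test 75.7%, 74.5% and 95.9%, in the same order.

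**Step 2: power with covariates.** If baseline covariates explain a share R² of outcome variance, the effective size is n/(1 − R²). Example, H2.2 at R² = 0.10: n = 80/0.90 = 88.9, se0 = 0.0740, se1 = 0.0722, z = (0.22 − 0.1451)/0.0722 = 1.04, power 85.0%. The documents give no R², so the range is an assumption.

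| Assumed R² | H2.2 | Social work | Resource center |
|---|---|---|---|
| 0 | 81.1% | 79.4% | 97.4% |
| 0.02 | 81.9% | 80.2% | 97.6% |
| 0.05 | 83.1% | 81.4% | 98.0% |
| 0.10 | 85.0% | 83.5% | 98.5% |
| 0.15 | 87.0% | 85.5% | 98.9% |
| 0.20 | 88.9% | 87.6% | 99.2% |

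**Step 3: simulation check.** 6,000 trials per setting, 80 per arm, logistic likelihood-ratio test with and without one prognostic score, marginal rates held at the plan's values. For a score with AUC of about 0.61, 0.67 or 0.73 (assumed), H2.2 power goes from 80–81% to 82.9%, 84.7% or 87.4%. Social work goes from 80–81% to 81.5%, 83.3% or 86.7%. This agrees with the table. In separate simulations, null rejection was between about 5% and about 6%, the higher figure with a likelihood-ratio test, so the smallest apparent gains should not be over-read.

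**Step 4: how many covariates the data can carry.** Expected events at the planning rates are 80×0.53 + 80×0.31 = 67.2 for H2.2 and 80×0.20 + 80×0.40 = 48 for social work. With intercept, arm and stratum, three covariates for H2.2 make six parameters (67.2/6 = 11.2 events each). Two covariates for H1.3 make five (48/5 = 9.6). A short list is supportable; a long one is not.

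**The case against.** *The predictors may be weak.* This stands. The documents give no R², AUC or odds ratio for these events. Section 2.1 reports that few caregivers use support services despite significant QOL problems, so need and use may be loosely linked, and section 2.4 says caregiver distress correlates with burden and QOL, so those covariates overlap. In a simulation with four weak covariates (linear-predictor SD 0.25), power moved only from 81.0% to 81.9% for H2.2 and from 80.0% to 80.4% for social work. A reader might infer that strong predictors are being ignored; the documents do not show that they are strong.

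*Missing covariates could cancel the gain.* This stands if incomplete cases are dropped. With 10% missing (assumed), H2.2 power went from 81.3% to 80.5% at a linear-predictor SD of 0.5, and from 81.6% to 82.2% at 0.8. It counts against relying on pulmonary function, which is abstracted on a form that Table 2 schedules at 3 months and whose completeness is not stated. Near-complete baseline items with imputation avoid the loss.

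*E.5 already has a propensity-score model.* In part. It covers medical and socio-demographic variables, but it is secondary and addresses imbalance rather than precision. One of its three covariables, the baseline value, does not exist here.

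*Section 13.1 promises extra power that these endpoints do not get.* A reader might infer this from the statement that the planned analysis "will adjust for baseline values, and will combine longitudinal assessments, both of which will improve power". That statement accompanies a t-test calculation based on an SD column, and the binary rows have no SD. Their stated power needs no covariates, and one yes/no drawn from several administrations may already combine assessments.

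**Conclusion.** The point holds as an efficiency improvement. The stratum-only analysis of H1.3 and H2.2 is valid and delivers the stated power under the pooled formula. Adjustment would add about 1 to 8 points for H2.2 and social work referrals if R² lies between 0.02 and 0.20, and under 2 points for resource-center use. The range is assumed, and the gain could be negligible.

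Three stronger readings are not supported:

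- *These endpoints have uniquely thin power.* FACT-L, activation and self-efficacy are also stated at 80%, and caregiver burden at 81%; resource-center use is at 97%.
- *Contacts before enrolment dilute the social work comparison.* The caregiver survey is not given at baseline, and if 10% had prior contact the rates would be 0.10 + 0.90×0.20 = 28% and 0.10 + 0.90×0.40 = 46%, with power 65.7%. But the 10% is invented, the survey's recall window is not shown, and the planning rates may already count any use.
- *The homogeneity test is a gate.* The plan places it before the overall test but states no consequence; the overall test appears to follow regardless.

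Separately, section 1.0 predicts lower social work referrals under H1.3, while E.5 predicts higher. The two must be reconciled; two-sided power is unaffected.

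**What to change.** Amend E.5 for H1.3 and H2.2 before outcomes are examined by arm:

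1. Name as primary a logistic regression with arm, randomisation stratum and two to four fixed, near-complete baseline covariates. For H2.2: age, comorbidity count and baseline FACT-L. For H1.3: baseline caregiver distress and burden. Naming the model also settles which test is used.
2. Use simple imputation of missing covariate values, done without regard to arm, so that no subject is dropped.
3. Report the standardised risk difference with its confidence interval.
4. Keep the stratum-only comparison as a sensitivity analysis, and report the stratum interaction descriptively.

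The cost is SAP wording, slightly more analysis work and a few extra parameters on about 160 subjects. No new data are needed. A new baseline service-use item is not proposed: it could not be obtained at baseline for dyads already enrolled.
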